PRIMO	PRIMO Study Protocol	CDC-00031 Rev. 03 Page: 1/1
--------------	---------------------------------------	-----------------------------------

PRIMO Study Protocol

Protocol Number: CDC-00031

NCT04843436

SPONSOR DOCUMENT APPROVALS

Role	Name / Function
Issuer	[name] Clinical Operations Project Manager, Clinical Affairs
Reviewer & Approver	[name] Associate Director, Clinical Affairs
Reviewer & Approver	[name] VP, Regulatory Affairs

Reference ARENA PLM for document approvals and approval date.

Revision History		
REV	DATE	DESCRIPTION
00	10MAR2020	N/A, first issue
1.0	17NOV2020	Modified from Observational to Post-market clinical study
2.0	20OCT2021	Updates in accordance to EU MDR 2017/745 and ISO 14155:2020; Follow-up visit for free flap, replantation and other procedures extended to 30±7 days
3.0	11AUG2022	Addition of protocol description

**RASM
POST MARKET CLINICAL FOLLOW-UP
STUDY
Synopsis**

CDC-00031
Rev. 03
Page: 1/4

**PRIMO: Post-Market, Non-Randomized, Multicentre PMCF Study To Monitor
The Safety And Performance Of Symani System In Microsurgical
Reconstructive Procedures In A Real Life Setting**

Protocol Synopsis

Study Objectives	The objective of this PMCF study is to monitor the safety, usability, performance and long-term efficacy of the Symani System.
Study Device	Symani System for Microsurgery (Symani)
Indication for Use	
The Symani System is a CE-marked device and it is intended for soft tissue manipulation to perform microsurgery techniques such as anastomosis, suturing, and ligation on small anatomical structures, including blood vessels and lymphatic ducts, in open surgery procedures.
 
The Symani System teleoperated-instruments are indicated for use during microsurgical procedures when use of a motion scaling function is deemed appropriate by the surgeon.
 
The Symani System is not intended for use on the heart, central circulatory system, central nervous system, or the eye. The system is indicated for adult and pediatric use, even if in the present study, only adult population will be enrolled. It is intended to be used by trained physicians in an appropriate operating environment in accordance with the Instructions for Use.

Study Design	
A prospective, single-arm, open-label, clinical study designed to evaluate the Symani System safety and effectiveness for microsurgical anastomosis.
 
The study will be conducted in at least 3 centers in Europe.

Target Population and sample size	The patients selected for this PMCF activity will be adults (over 18 years) requiring microsurgical reconstructive procedures applied to arterial, venous, neural or lymphatic anastomosis. The planned minimum sample size is 402 patients to ensure lower 95% confidence limit for the Primary Endpoint. A drop out rate of 5% will allow to include a total of 420 subjects. All subjects will be enrolled and followed in at least 3 EU centres until the sample size is reached.

**RASM
POST MARKET CLINICAL FOLLOW-UP
STUDY
Synopsis**

CDC-00031
Rev. 03
Page: 2/4

Duration of Study	Each enrolled subject will be followed through the first 30±7 days post-operatively or 24 weeks post-operatively (according to the procedures) per the follow-up schedule reflecting the standard of care.
Primary Endpoint	The primary endpoint will be defined as the ability to complete the surgical task with Symani as intended by the surgeon. This endpoint will be referred to as “Procedure Robotic Success”.
Secondary Endpoints	
The main secondary endpoint will be the rating of the surgeon experience of robot usability, which will be assessed using a questionnaire.
 
Further secondary endpoints will be assessed regarding the clinical outcome of the procedures. These criteria will differ depending on the procedure performed being a replantation, free flap surgery, lymphatic surgery or other.
 
Replantations
 
• Time for each anastomosis execution and warm ischemia time (minutes)• Intraoperative need to redo the anastomosis (yes or no)• Postoperative need to redo within 7 days (complication and need to return to the operating room to explore anastomosis: yes or no)• Complications• Replantation Failure or Loss (subsequent amputation) 
Free Flaps
 
• Time for each anastomosis execution and warm ischemia time (minutes)• Intraoperative need to redo the anastomosis (yes or no)• Postoperative need to redo within 7 days (complication and need to return to the operating room to explore anastomosis: yes or no)• Complications• Flap Failure or Loss (yes or no) 
Lymphatic Surgery
 
• Time for each anastomosis execution (in minutes)• Intraoperative need to redo based on ICG Patency (yes or no)• Postoperative need to redo based on ICG Patency (yes or no)• Complications• Limb volume reduction

**RASM
POST MARKET CLINICAL FOLLOW-UP
STUDY
Synopsis**

CDC-00031
Rev. 03
Page: 3/4

	
Immediate and postoperative complications including arterial insufficiency, venous congestion, thrombosis, need for surgical re-exploration of anastomosis, partial flap necrosis or flap loss will be recorded. In the case of lymphatic surgery, the Surgeon will use volumetric measurement to assess the procedure impact on lymphedema.
 
All adverse events will be collected from the procedure date to the study exit of each subject enrolled.

Analysis	
The full analysis set (FAS) is defined as all patients enrolled onto the registry who underwent surgery with Symani. The FAS will be sub-divided into three distinct cohorts, depending on the surgery performed (replantation, free flaps, lymphatic surgery).

Follow-Up Schedule	
Assessments will be made intraoperatively and at regular intervals during hospitalization.
 
The study will be considered complete after all patients have completed their follow-up visits as described in the study protocol.

Inclusion and Exclusion Criteria	
Inclusion criteria
 
1) Male and female patients aged >182) Patients who need a reconstructive procedure and a microsurgical reconstruction is deemed the best option by the plastic, orthopedic or other surgeon in response to a post-oncological, post-traumatic or congenital tissue defect or to treat lymphedema.3) Patients who have been selected by the PI at the Clinical Center as appropriate candidates for treatment with Symani System in accordance with the IFU.4) Subjects who fit the criteria to perform surgery requiring reconstructions using free flaps, replantation, lymphatic reconstructions.5) Subjects who agree to have the surgery and the anaesthesia.6) Subjects who voluntarily decide to participate in this study with the surgery performed with the aid of the Symani System and sign the Informed Consent Form. 
Exclusion criteria
 
1) Subjects who have bleeding or coagulation disorders in the past or present.2) Any criteria that preclude prolonged anesthesia.3) History of anaphylaxis or severe complicated allergy symptoms.

**RASM
POST MARKET CLINICAL FOLLOW-UP
STUDY
Synopsis**

CDC-00031
Rev. 03
Page: 4/4

- 4) Clinically significant cardiovascular, digestive, respiratory, endocrine, or central nervous system disorders or previous mental disorders that may significantly affect the data collection or the ability to comply with the protocol.
- 5) Evidence or history of autoimmune disease or compromised immune system.
- 6) Participation in another clinical trial within 4 weeks prior to participation in the study.
- 7) Subjects belonging to vulnerable populations or ineligible to participate for other reasons by the PI at a Clinical Center.
- 8) Subjects with pacemaker.

1. OVERVIEW AND INVESTIGATIONAL PLAN

1.1 Study design

The PRIMO study is a prospective, non-randomized, single arm, multicenter, post-market clinical follow-up (PMCF) study designed to evaluate the safety and effectiveness of the Symani System when used to assist microsurgical anastomoses in the real-world setting: i.e. it is a real world prospective observational data collection process. Patients selected will include adults (over 18 years) requiring microsurgical reconstructive procedures applied to arterial, venous, neural, or lymphatic anastomosis. Patients will be enrolled, undergo surgery, and have assessments made at regular intervals (day 1, day 4, day 14, day 30 (free flap), and 24 weeks (lymphatic anastomoses)).

An addendum to the PRIMO study was prepared and approved in December 2022. The addendum describes the addition of retrospective data collection to the PRIMO study. This will include patients with the same profile as the prospective data collected in the PRIMO study (i.e. ≥ 18 years requiring microsurgical reconstructive procedures applied to arterial, venous, neural, or lymphatic anastomosis) and will collect as much data as possible (based on availability) using the same data collection process as for the prospective data collection. Accordingly, the PRIMO study describes two data sources (prospective data collection and retrospective data collection), both collected under a common protocol. There will be some case report forms defined for prospective data collection (in the PRIMO protocol), specifically nurse and clinician questionnaires, which will not be available for the data collected retrospectively (in the PRIMO addendum).

1.2 Purpose of this Statistical Analysis Plan (SAP)

This SAP describes endpoints to be analyzed for the PRIMO study, using data collected prospectively and retrospectively, where available, for all patients.

The purpose of this SAP is to provide a detailed description of the methods of analysis to be used for the PRIMO study endpoints.

1.3 Study Objectives

The objective of the PRIMO study is to monitor the safety, usability, performance, and long-term efficacy of the Symani System.

1.3.1 Endpoints

Primary endpoint

The primary endpoint is defined as the ability to complete the surgical task with Symani as intended by the surgeon. This endpoint will be referred to as "Procedure Robotic Success".

Sponsor: MMI Product: Symani system for microsurgical anastomosis Study: PRIMO	
Statistical Analysis Plan Final 22 November 2024	

Secondary endpoints

The main secondary endpoint will be the rating of the surgeon's experience of robot usability, which will be assessed using the usability questionnaire.

Further secondary endpoints will be assessed regarding the clinical outcome of the procedures (e.g. time for each anastomosis). Some of these endpoints may differ depending on the procedure performed (replantation, free flap surgery, lymphatic surgery or other).

Replantation

- Time for each anastomosis execution or nerve coaptation
- Warm ischemia time (minutes)
- Intraoperative need to redo the anastomosis (yes or no)
- Postoperative need to redo within 7 days (Complication and need to return to the operating room to explore anastomosis: yes or no)
- Complications
- Replantation Failure or Loss (subsequent amputation)

Free Flaps

- Time for each anastomosis execution
- Warm ischemia time (minutes)
- Intraoperative need to redo the anastomosis (yes or no)
- Postoperative need to redo within 7 days (Complication and need to return to the operating room to explore anastomosis: yes or no)
- Complications
- Flap Failure or Loss (yes or no)

Lymphatic Surgery

- Time for each anastomosis execution (in minutes)
- Intraoperative need to redo based on ICG Patency (yes or no)
- Postoperative need to redo based on ICG Patency (yes or no)
- Complications
- Limb volume reduction

Sponsor: MMI Product: Symani system for microsurgical anastomosis Study: PRIMO	
Statistical Analysis Plan Final 22 November 2024	

1.3.2 Safety endpoints

The complications as indicated above, will be collected as adverse events (AE, SAE/ADE/SADE/ADE/DD) reported by patients or evaluated by the Surgeon from day 0 to either 30 days after surgery for free flaps, replantation and other procedures, or 24 weeks after surgery for the LVA procedures will be recorded.

1.4 Relevant study documents

- Protocol: CDC-00031 PRIMO Clinical Investigation Plan Rev. 03
- Addendum to protocol: CDC-00031 Rev03 - Addendum to PMCF Protocol for retrospective data collection Rev.01.pdf
- CRF Dendrite: CDC-00085 RASM PMCF Case Report Forms
- CRF Castor: CDC-00124 PRIMO Case Report Forms_Rev03

Note: Prospective patients enrolled prior to 01FEBRUARY2023 were collected in electronic data capture (EDC) Dendrite Clinical System (Dendrite). Prospective patients enrolled post 01FEBRUARY2023 were collected in the EDC Castor. All retrospective patients' data will be collected in the EDC Castor. Both EDC Case Report Forms contain the same data elements; however, the names and format of the CRFs have been revised in Castor for ease of use.

1.5 Modifications from the statistical section of the protocol

Modification to the definition of the FAS to only include patients who had at least one robotic suture placed.

Definition of a safety set to be all patients with at least one robotic suture attempted.

Amendment to the sample size section to note analysis at the anastomosis level and to remove notes about missing data as this is handled under data derivations.

Amendment to the sample size section to note that the total sample specified in the PRIMO study protocol can be achieved through prospective or retrospective patients. That is, the data of retrospective patients is now included in the target sample size.

Amendment to the analysis of the primary effectiveness endpoint to be at the anastomosis level rather than at the patient level.

Amendment to the analysis of anastomosis time to use a mixed model rather than a KM analysis. This change has been made since all anastomoses will have a time, so a specific 'time to event' analysis (eg KM) is not needed as there are no censored times. Using a mixed model will allow adjustment for the dependence in the data.

Definition of some additional efficacy endpoints namely:

- Free flap viability at 30 days
- Intra-operative anastomosis patency

Definition of some additional safety endpoints namely:

- Freedom from device related serious adverse events prior to discharge

Sponsor: MMI Product: Symani system for microsurgical anastomosis Study: PRIMO	
Statistical Analysis Plan Final 22 November 2024	

- Freedom from device related adverse events prior to discharge
- All cause re-admission rates
- All cause re-operation rates up to 30 days
- All cause mortality rates up to 30 days

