1.7 Determination of sample size

The planned minimum sample size is 402 patients. The primary endpoint for the study is technical performance, assessed as a binary outcome procedural success Yes/No. Procedural success will be assessed at the anastomosis level; each patient may have > 1 anastomosis. Based on data published in the medical literature (see RASM Literature Review Report [5]), the traditional failure and complication rate for vascular anastomoses is 15%, implying a success rate of 85%. The study will have 85% power to conclude that a success rate using Symani of 89% (or higher) is better than the literature value if a minimum of 402 anastomoses operations are performed. The percentage success will be estimated and exact 95% confidence limits calculated. If the lower 95% confidence limit exceeds 85% then the conclusion can be reached that Symani is superior to manual surgical methods. As each patient may have more than one anastomosis operation, the number of anastomoses will be ≥ 402 from 402 patients, providing increased power. As the number of anastomoses/patient is unknown at the time of study design, the conservative approach of recruiting 402 patients has been followed.

The number of patients missing a response for the primary endpoint will be monitored and additional patients may be recruited if deemed necessary.

There will be no predetermined limit to the number of sites that can participate in the study. Patients enrolled under the retrospective data collection protocol addendum will contribute to the planned sample size for the entire study (prospective plus retrospective).

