2.1.3.1 Primary effectiveness endpoint – Procedure Robotic Success

Form R or Anastomosis Data Form will be completed for each anastomosis. If the answer to the question 'How did you intend to perform this anastomosis' is 'Robotic' then the anastomosis is included for this endpoint.

The endpoint will be derived for each anastomosis using the question "Did you experience any system technical issues resulting in unplanned return to conventional suturing".

If the response is 'No' and the number of robotic sutures is > 0 or the number of robotic redo sutures is > 0, the anastomosis will be classified as 'intra-operative change from robotic to manual' = 'no'.

If the response is 'yes' anastomosis will be classified as intra-operative change from robotic to manual = 'yes'.

If there is no response to the question the anastomosis classification will be missing.

If the planned approach was manual the result will be N/A

The unit of analysis for this endpoint is the anastomosis.

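### Procedure Robotic Success is scored only per anastomosis, so the plan never reports the share of procedures or patients completed robotically

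*SAP*

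**What the plan says.** The protocol synopsis states: "The primary endpoint will be defined as the ability to complete the surgical task with Symani as intended by the surgeon". SAP 1.3.1 repeats the definition and the name. The synopsis sizes the study in patients: "The planned minimum sample size is 402 patients to ensure lower 95% confidence limit for the Primary Endpoint".

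The SAP moves to a lower level. Section 1.5 lists the change: "Amendment to the analysis of the primary effectiveness endpoint to be at the anastomosis level rather than at the patient level". Section 1.7 follows it: "Procedural success will be assessed at the anastomosis level; each patient may have > 1 anastomosis". Section 2.1.3.1 derives the outcome from one question on each robotic-intended anastomosis, about system technical issues that forced an unplanned return to conventional suturing, and ends: "The unit of analysis for this endpoint is the anastomosis". Section 2.4.4.1 uses the number of anastomoses as the denominator, and Appendix 1 lists robotic success at that level only.

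The benchmark also comes from section 1.7: "the traditional failure and complication rate for vascular anastomoses is 15%, implying a success rate of 85" percent. If the lower 95% limit exceeds 85%, the SAP concludes that Symani is superior to manual methods.

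**The concern.** The SAP's own hierarchy (section 2, Figure 1) places anastomoses below procedures, and the note to Figure 2 defines a procedure as a flap, a replantation or a lymphatic procedure. The endpoint carries a procedure name and the protocol analysed it per patient, yet the counted unit is now the lowest level. Take a procedure with three robotic-intended anastomoses, one of them converted for a technical issue. The SAP records two successes and one failure. If completing the task means completing all of it, the procedure was not completed with the robot.

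What is at stake is what the headline number means. A reader who sees a percentage under the name Procedure Robotic Success will take it as the share of procedures, or patients, in which the robotic plan was carried through. The SAP cannot supply that share.

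**Working it through.** **1. The plan's own figure.** Inputs from SAP 1.7: null 85%, alternative 89%, n = 402, exact 95% limits, success if the lower limit exceeds 85%. Sidedness is not stated; I take two-sided limits. The Clopper-Pearson lower limit first exceeds 85% at 356/402 (88.6%). P(X ≥ 356 | n = 402, p = 0.89) = 64.9%, not the stated 85%. With one-sided 5% limits the count is 354 and power 75.6%. At a true rate of 90% the two-sided rule gives 85.2%. This mismatch is a separate matter. Only the decision rule is used below.

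**2. Is there a roll-up anywhere?** Section 2.1.3.1 scores each anastomosis as changed or not changed from robotic to manual; I read not changed as success. Section 2.4.4.1 tabulates and models those scores by surgery type. The mixed model handles dependence but still estimates a rate per anastomosis. Appendix 1 adds no other level. The only patient-level item on procedural success is the surgeon's questionnaire rating (2.1.3.2.1), which is subjective and collected for prospective patients only.

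**3. How far apart can the two rates be?** Anastomoses per patient (m) are described in SAP 1.7 as unknown, and no within-patient correlation (ρ) is given. Both are assumed here, as is the rule that every robotic-intended anastomosis must succeed. For m = 1 the rates are identical. For m = 2 with success rate p per anastomosis,

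P(both succeed) = p² + ρ·p·(1 − p).

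| p (assumed) | ρ = 0 | ρ = 0.2 | ρ = 0.4 |
|---|---|---|---|
| 0.89 | 79.2% | 81.2% | 83.1% |
| 0.92 | 84.6% | 86.1% | 87.6% |
| 0.95 | 90.3% | 91.2% | 92.2% |
| 0.97 | 94.1% | 94.7% | 95.3% |

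For example, 0.92² = 0.8464, and 0.4 × 0.92 × 0.08 = 0.0294, which sum to 0.8758. If only 25% of patients have two anastomoses, with p = 0.92 and ρ = 0, the patient-level rate is 0.75 × 0.92 + 0.25 × 0.8464 = 90.2%.

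**4. The same point at the pass mark.** With 402 patients and two anastomoses each (n = 804), the exact lower limit first exceeds 85% at 704/804 (87.6%), leaving 100 failures. If these fall in 100 different patients, 302/402 = 75.1% of patients have both completed. If they fall in pairs in 50 patients, the figure is 352/402 = 87.6%. The anastomosis result alone cannot distinguish these cases.

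**5. Does the change of unit ease the claim?** Keep 402 patients and m = 2. The table gives the probability that the exact rule passes. The per-anastomosis column treats the 804 as independent; patient-level columns are for ρ = 0 / 0.2 / 0.4. The matched bar is what 85% per anastomosis implies per patient: 0.85² + ρ × 0.85 × 0.15 = 72.3% / 74.8% / 77.4%.

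| p | Per anastomosis, bar 85% | Per patient, bar 85% | Per patient, matched bar |
|---|---|---|---|
| 0.89 | 0.91 | below 0.01 throughout | 0.89 / 0.84 / 0.81 |
| 0.92 | about 1.00 | 0.015 / 0.09 / 0.31 | about 1.00 throughout |
| 0.95 | about 1.00 | 0.89 / 0.97 / 0.996 | about 1.00 throughout |

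Allowing for correlation lowers the 0.91 only slightly, to 0.89 at ρ = 0.2 (simulation).

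**The case against.** The best defence is that the SAP's unit fits its benchmark. Section 1.7 takes 85% from vascular anastomoses, so comparing anastomoses with it is coherent, and the change is disclosed in section 1.5. The protocol synopsis has no rule for a patient with mixed results, and it describes the study as evaluating Symani for microsurgical anastomosis. Intent is also recorded anastomosis by anastomosis, so the task could be read as the single anastomosis.

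Much of this stands. A reader might infer that the SAP kept the protocol's 85% bar, moved to an easier unit, and so made the claim far easier to pass. The documents do not support that. The supplied protocol states no 85% threshold, so an unchanged bar cannot be shown. The large contrast in step 5 comes mostly from holding an all-must-succeed patient score to a per-anastomosis bar. It largely disappears against a matched bar, and it shrinks at 95% success even against the unmatched one. For the same reason, requiring the lower limit to exceed 85% for procedures or patients would be unjustified on the present material.

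The objection does not explain why the protocol's patient-level analysis was dropped, nor does it supply a procedure- or patient-level result. Agreement with the benchmark supports reporting an anastomosis rate; it does not support reporting it under a procedure name. Disclosing the change does not cure that.

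**Conclusion.** The point holds as one about what is estimated and how it is labelled. The SAP replaces a patient-level endpoint with an anastomosis-level rate under the same name and plans no result at the level that the name and definition suggest. That much follows from the text without any assumption about data.

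The numerical gap is conditional. It is zero with one anastomosis per patient. With two each, it is about 6 to 10 percentage points at 89% success per anastomosis, 4 to 7 at 92%, and 2 to 3 at 97%, for ρ from 0.4 down to 0. These figures assume that one technical conversion fails the patient, which is the natural reading of completing the task but is not written in the supplied protocol. Only conversions for system technical issues count as failures here, as in SAP 2.1.3.1.

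The planned test against 85% remains usable as a statement about anastomoses. It should not be read as one about procedures or patients.

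**What to change.** - Derive two further variables, one per procedure and one per patient: Yes only if every robotic-intended anastomosis in that unit is scored as completed robotically. State how a unit with an unanswered anastomosis question is classified.
- Report both with 95% limits as the result for the protocol-defined endpoint, overall and by surgery type. Model 4, already specified for procedure-level outcomes, can serve the procedure-level rate.
- Rename the existing result anastomosis-level robotic success in SAP 2.1.3.1, 2.4.4.1 and Appendix 1, and give the reason for the change of unit in section 1.5.
- Word the 85% conclusion in section 1.7 as applying to anastomoses. Apply no threshold to procedures or patients unless a benchmark for that unit is justified.

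The cost is SAP wording and one derivation at two levels from data already collected, with no new data collection. The downside is a less favourable headline rate wherever patients have several anastomoses.
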